10.1.1.2 Secondary Endpoint(s)

Key Secondary Endpoints (phase 3 only):

- Overall Survival (OS): calculated as the time from the date of randomization until death due to any cause. Subjects who are alive at the date that triggers the analysis will be censored at the date last known to be alive. If the date last known to be alive is after the date that triggers the analysis, the subject will be censored at the analysis trigger date.

Other Secondary Endpoints:

Phase 2:

- Objective response rates (ORR **including** CMR and PMR)
- PFS: calculated as the time from start of blinatumomab until the date of diagnosis of progression of lymphoma, or date of death, whichever is earliest. Subjects who are alive and did not have progression will be censored at the last date of tumor assessment.
- DOR: calculated only for subjects who achieve an OR. The duration will be calculated from the date a response, CMR or PMR, is first achieved **per central review during the first 12 weeks after starting blinatumomab** until the earliest date of a disease assessment indicating a relapse event or death, whichever occurs first. Subjects who do not have a relapse event will be censored on their last disease assessment date. If the last disease assessment date is after the date that triggers the analysis, the subject will be censored at the analysis trigger date. A sensitivity analysis will censor subjects who receive a HSCT at the time of HSCT unless there is no assessment after the HSCT, in which case the last assessment prior to the HSCT will be used as the censoring time. **Disease assessment during LTFU will be reviewed by investigators only per central review agreement.**
- Successful mobilization rate (defined as CD34+ cell $2 \times 10^6/\text{kg}$)
- HSCT (both autologous and allogeneic) rates among subjects with post-blinatumomab CMR+PMR
- 100-day non-relapse mortality (NRM) after HSCT
- Blinatumomab steady state concentration and clearance
- Incidence and severity of treatment-emergent adverse events

Phase 3:

- OR (**including** CMR and PMR)
- PFS: calculated as the time from the date of randomization until the date of diagnosis of progression of lymphoma, or date of death, whichever is earliest. Subjects who are alive and did not have progression will be censored at the last date of tumor assessment.
- DOR
- Successful mobilization rate (defined as CD34+ cell $2 \times 10^6/\text{kg}$) following protocol assigned therapy

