10.1.2.1 AutoHSCT Analysis Set

Includes all subjects who achieve a response and undergo autoHSCT **while in remission and without any other anti-cancer treatment.**

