10.5.3 Secondary Efficacy Endpoint(s)

Phase 2:

Other secondary efficacy endpoints include OR after **initiation** of blinatumomab and during the treatment, PFS, duration of CMR, DOR, successful mobilization rate, alloHSCT rate, autoHSCT rate and 100-day NRM after autoHSCT.

OR **during the first 12 weeks after initiation of** blinatumomab during the treatment will be summarized with an exact binomial 95% confidence interval.

PFS will be summarized with the KM summaries.

Duration of CMR and duration of response will be summarized with the KM summaries in Responders Analysis Set.

Successful mobilization rate, autoHSCT rate and alloHSCT rate will be summarized with an exact binomial 95% confidence interval. AutoHSCT rate will be analyzed using autoHSCT Analysis Set.

The 100-day NRM after autoHSCT rate will be summarized with the cumulative incidence function with **relapse or deaths due to relapse** treated as competing risks. For this endpoint, time to non-relapse deaths will be measured starting from the date of autologous HSCT.

Phase 3:

OS is the key secondary efficacy endpoint for Phase 3. A 1-sided stratified log-rank test, stratified by the randomization factors, will be used to determine if OS is superior in the

blinatumomab arm compared to IC arm when the 236th death in phase 3 subjects is reported. In addition, a hazard ratio with a 2-sided 95% confidence interval will be estimated from a stratified Cox regression model. The KM summaries will be performed by treatment group.

Other secondary efficacy endpoints include OR, PFS, duration of CMR and ORR, successful mobilization rate, HSCT rate, 100-day NRM after HSCT rate. Overall response rate will be summarized by treatment group with an exact binomial 95% confidence interval. For descriptive purposes, a 1-sided Cochran-Mantel-Haenszel test, which will adjust for the stratification factors at randomization, will test if the blinatumomab arm has a higher ORR compared to the IC arm. PFS, duration of CMR and the duration of ORR will be summarized with the KM summaries by treatment group. For descriptive purposes, a stratified log-rank test, stratified by the randomization factors, will be provided. A hazard ratio with a 2-sided 95% confidence interval will be estimated from a stratified Cox regression model.

Successful mobilization rate and HSCT rate will be summarized by treatment group with an exact binomial 95% confidence interval.

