6.2 Efficacy Endpoints

Response rate will be based on the central review of radiographic assessment of PET-CT scans using the Lugano Classification. DOR, DOCR, PFS and HSCT related endpoints will be based on investigator's review of radiographic assessment of PET-CT scans using the Lugano Classification and clinical assessment.

100 Day non-relapse mortality (NRM) Rate after HSCT

Non-relapse mortality rate at 100 days after HSCT will be estimated using the cumulative incidence function with relapse or deaths due to relapse treated as competing risks. Only subjects who achieve a response **per investigator's review** and undergo autoHSCT are included. Only deaths without relapse are considered as events.

Allogeneic HSCT (alloHSCT) Rate

Allogeneic HSCT rate is the proportion of responder **per investigator's review** (subjects who achieved either CMR or PMR during the treatment) who have undergone alloHSCT **while in remission and without any other anti-cancer treatment**.

Autologous HSCT (autoHSCT) Rate

Autologous HSCT rate is the proportion of responder **per investigator's review** (subjects who achieved either CMR or PMR during the treatment) who have undergone autoHSCT **while in remission and without any other anti-cancer treatment**

Complete Metabolic Response (CMR)

CMR is determined by the central review of radiographic assessment of PET-CT scans using the Lugano Classification. Subject's CMR status is determined by whether the subject achieves CMR during the first 12 weeks of treatment since starting blinatumomab.

Complete Metabolic Response Rate (CMR Rate)

Complete metabolic response rate (CRR) is the proportion of subjects who have achieved CMR by the central review of radiographic assessment of PET-CT using Lugano Classification among all subjects in the respective analysis set.

Duration of Response (DOR)

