Duration of Response is calculated only for subjects who achieve a response (CMR or PMR) per **investigator's** review during the first **12 weeks** starting blinatumomab. The duration will be calculated from the date a response, CMR or PMR, is first achieved until the earliest date of a disease assessment indicating disease progression or death, whichever occurs first. **For diagnosis of progression of lymphoma, the progression per investigator's review of radiographic assessment of PET-CT using Lugano Classification will be used. In the absence of radiographic assessment during the long term follow up period, the clinical progression on the CRF page will be used.** Subjects who do not have a relapse event will be censored on their last **radiological non-missing evaluable tumor assessment date or last non-missing clinical assessment**. If the last disease assessment date is after the date that triggers the analysis, the subject will be censored **at the last radiological non-missing evaluable tumor assessment date or last non-missing clinical assessment** prior to the analysis trigger date. A sensitivity analysis will censor subjects who receive a HSCT at the time of HSCT unless there is no assessment after the HSCT, in which case the last **clinical or radiological non-missing evaluable tumor assessment** prior to the HSCT will be used as the censoring time.

HSCT Rate

HSCT rate is the proportion of responder per investigator's review (subjects who achieved either CMR or PMR during the treatment) who have undergone alloHSCT or autoHSCT while in remission and without any other anti-cancer treatment.

Objective Response (OR)

OR is determined **by the central review of radiographic assessment of PET-CT using Lugano Classification**. Subject's ORR status is determined by whether the subject achieves OR (CMR or PMR) during the first 12 weeks of treatment since starting blinatumomab.

Objective Response Rate (ORR)

Objective response rate (ORR) is the proportion of subjects who have achieved an OR (CMR or a PMR) **by the central review of radiographic assessment of PET-CT using Lugano Classification** among all subjects in the respective analysis set.

Overall Survival (OS)

It is calculated as the time from the first dose of blinatumomab until death due to any cause. Subjects who are alive at the date that triggers the analysis will be censored at the date last known to be alive.

Progression Free Survival (PFS)

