10.5.2 Analyses of Secondary Efficacy Endpoint(s)

Other secondary efficacy endpoints include ORR during the first 12 weeks of starting blinatumomab and during the treatment, PFS, duration of CMR, duration of response, successful mobilization rate, alloHSCT rate, autoHSCT rate and 100-day NRM after HSCT.

ORR during the first 12 weeks after initiation of blinatumomab and during the treatment will be summarized with an exact binomial 95% confidence interval.

PFS and OS will be summarized with the KM summaries.

Duration of CMR and duration of response will be summarized with the KM summaries using Responder Analysis Set.

AutoHSCT rate, alloHSCT rate and HSCT rate will be summarized with an exact binomial 95% confidence interval. AutoHSCT rate is the proportion of all subjects who achieve a response per investigator's review and undergo autoHSCT while in remission and without any other anti-cancer treatment, eg, all subject in the autoHSCT Analysis Set. Similarly alloHSCT rate will be analyzed with subjects in the alloHSCT Analysis Set. HSCT rate will be analyzed with subjects who are in either autoHSCT or alloHSCT Analysis Set. The rates are based on Responder Analysis Set. As a sensitivity analysis, HSCT (autoHSCT or alloHSCT) rate will be provided with the proportion of all subjects who had HSCT based on FAS.

Successful mobilization rate will be summarized based with an exact binomial 95% confidence interval. Successful mobilization rate is the proportion of subjects who initiated mobilization while in remission and without any other anti-tumor therapy, and the mobilization procedure has an outcome as 'Successful' as recorded on the mobilization CRF page based on Responder Analysis Set. As a sensitivity analysis, the proportion of subjects who initiated mobilization and the mobilization procedure

has **an** outcome as 'Successful' **as** recorded on **the** mobilization CRF page based on FAS will be provided.

The 100-day NRM after HSCT rate **based on subjects either in autoHSCT analysis set or alloHSCT analysis set** will be summarized with the cumulative incidence function with relapse or deaths due to relapse treated as competing risks. For this endpoint, time to non-relapse deaths will be measured starting from the date of HSCT.

10.5.3 Analyses of Patient Reported Outcomes and Other Health Related Quality of Life Endpoints

Not Applicable.

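### Protocol 10.5.3 analyses the phase 2 autoHSCT rate in a set made up only of autoHSCT recipients, so as written the rate is always 100%; the SAP uses responders but muddles numerator and denominator.

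*Protocol*

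**What the plan says.** **Protocol.** Section 10.1.1.2 lists as a phase 2 secondary endpoint "HSCT (both autologous and allogeneic) rates among subjects with post-blinatumomab CMR+PMR", so the denominator is responders. Section 10.5.3 then gives the analysis: "AutoHSCT rate will be analyzed using autoHSCT Analysis Set". Section 10.1.2.1 defines that set: "Includes all subjects who achieve a response and undergo autoHSCT", with the added conditions of being in remission and having had no other anti-cancer treatment. Section 10.5.3 names no analysis set for the phase 2 alloHSCT rate or the phase 3 HSCT rate.

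**SAP.** Section 6.2 defines each rate over responders by investigator review, counting CMR or PMR at any time during treatment: "Autologous HSCT rate is the proportion of responder", the same for alloHSCT, and "HSCT rate is the proportion of responder per" investigator review for either transplant. Section 10.5.2 first equates the autoHSCT rate with the subjects in the autoHSCT Analysis Set and continues: "Similarly alloHSCT rate will be analyzed with subjects in the alloHSCT Analysis Set" and "HSCT rate will be analyzed with subjects who are in either autoHSCT or alloHSCT Analysis Set". It then says "The rates are based on Responder Analysis Set" and adds a sensitivity analysis of HSCT over the FAS. Sections 7.1 and 7.2 define the two transplant sets by investigator-reviewed response. Section 7.5 defines the Responder Analysis Set by central review in the first 12 weeks. Section 11 reports a change of reviewer but no change of denominator.

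**The concern.** Everyone in the autoHSCT Analysis Set has had an autoHSCT. A transplant rate computed in that set has the same subjects above and below the line and carries no information about how many responders reached transplant. The trial enrols subjects intended for high-dose therapy and autologous transplant (inclusion criterion 109), so this is one of the more clinically relevant secondary results.

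The SAP raises a second, smaller problem. It names transplant sets and a responder set for the same rates without saying which is numerator and which is denominator, and the sets rest on different reviewers and windows. A programmer following 10.5.2 could build a fraction whose numerator includes subjects missing from its denominator.

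**Working it through.** **Plan's own figure.** The documents state no HSCT rate or count. The only phase 2 design figure is 90% power with 36 subjects for CMR of 15% versus 40% at one-sided 0.025. It reproduces: the exact binomial test rejects at 11 or more CMRs, with size 0.0137 and power 0.910. The present point does not depend on it.

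**Step 1: the protocol sentence taken literally.** Let x be the number of subjects in the autoHSCT Analysis Set. All x had autoHSCT, so the rate is x/x = 100% for x ≥ 1 and undefined for x = 0. When all subjects are counted as events, the exact 95% interval is 0.025^(1/x) to 100%, so only its lower limit moves:

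| x | Rate | Lower 95% limit |
|---|---|---|
| 2 | 100% | 15.8% |
| 4 | 100% | 39.8% |
| 5 | 100% | 47.8% |
| 8 | 100% | 63.1% |

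**Step 2: the endpoint as defined.** Let R be the number of responders, so that the rate is x/R. R and x are assumptions here.

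| R | x | Rate x/R | Exact 95% CI |
|---|---|---|---|
| 9 | 4 | 44.4% | 13.7–78.8% |
| 15 | 4 | 26.7% | 7.8–55.1% |
| 16 | 5 | 31.3% | 11.0–58.7% |
| 20 | 4 | 20.0% | 5.7–43.7% |

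Over the FAS, taking all 36 planned subjects as treated, x = 4 gives 4/36 = 11.1% (3.1–26.1%). With R = 15, going from 2 to 4 to 8 transplants moves the responder-based rate from 13.3% to 26.7% to 53.3%. The protocol sentence returns 100% in all three cases.

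**Step 3: the SAP's sets side by side.**

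| Set or definition | Reviewer | Response window |
|---|---|---|
| Rates, SAP 6.2 | Investigator | During treatment |
| AutoHSCT and alloHSCT sets, SAP 7.1–7.2 | Investigator | Not stated |
| Responder Analysis Set, SAP 7.5 | Central | First 12 weeks |

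A subject called PMR by the investigator but not by central review, who then has autoHSCT in remission, is in the autoHSCT set but not in the Responder Analysis Set. If one of 5 transplanted subjects is such a case and there are 16 central responders (assumed), the fraction is 5/16 = 31.3% if the transplant set is the numerator, but 4/16 = 25.0% if the numerator is confined to the Responder Analysis Set. SAP 10.5.2 does not say which.

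**The case against.** The strongest reply is that the SAP governs the analysis and settles the denominator. Section 6.2 defines all three rates as proportions of responders, 10.5.2 states a responder base, and the FAS sensitivity analysis cannot be 100% by construction. On the most coherent reading of 10.5.2, the transplant sets identify the numerator. This stands. A reader might infer from the repeated wording that the SAP's alloHSCT and any-HSCT rates are also fixed at 100%, or that the SAP sets two rival denominators. The documents do not support either inference: the SAP text is confused, but its definitions point to responders.

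It can also be said that the protocol's endpoint definition in 10.1.1.2 already separates a low transplant rate from a high one, so only one sentence is at fault. That is right about scope, but it leaves the sentence in conflict with the definition. Reading the protocol's set as a mere numerator is hard to sustain: Section 10.1.2.3 uses the same form of words for the Target Dose Analysis Set, where the set is the population analysed, and 10.5.3 supplies no other denominator for the autoHSCT rate.

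Finally, these rates are descriptive. No test, alpha or phase 3 decision is attached to them; advancement rests on CMR. That also stands, and it limits the weight of the point.

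**Conclusion.** The protocol sentence is wrong as written: with at least one transplant it yields 100% whatever the data, against the protocol's own endpoint. That fault is limited to the phase 2 autoHSCT rate.

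The SAP does not carry the 100% result forward. What remains there is wording that blurs numerator and denominator for the transplant rates, and a mismatch of reviewer and window that leaves the numerator free to fall outside the denominator. It would go too far to say that the trial cannot tell few transplants from many, because the endpoint definition and the SAP definitions both can.

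The 100% result follows from the set definition alone. All the responder and transplant counts used to show its size, including 5/5 against 5/16, are assumptions. The primary CMR analysis is unaffected.

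**What to change.** - **Protocol 10.5.3:** replace the sentence on the autoHSCT rate. The numerator is subjects in the autoHSCT Analysis Set. The denominator is all responders, by the same reviewer and over the same window as the numerator. Report with an exact 95% CI.
- **SAP 10.5.2:** reword the sentences that place the rates in the transplant sets in the same way. The numerator is the autoHSCT set, the alloHSCT set, or either. The denominator is responders as in SAP 6.2 (investigator review, CMR or PMR during treatment), in place of the centrally reviewed Responder Analysis Set.
- **SAP 7.1 and 7.2:** state the response window so that each transplant set is a subset of that denominator.
- **Keep** the FAS-based sensitivity analysis. Use the transplant sets as a denominator only for post-transplant outcomes such as 100-day NRM.
- **SAP Section 11:** list the change of denominator from protocol 10.5.3.

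The cost is wording in two documents and a small programming check. No new data are needed, and the sample size and primary analysis do not change.

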10.5.4 Safety Endpoints

10.5.4.1 Adverse Events

The Medical Dictionary for Regulatory Activities will be used to code all adverse events (AE) to a system organ class and a preferred term. AEs of interest (EOI) categories will be based on search strategies defined by Medical Coding. All adverse event tables will be summarized by treatment group. Treatment-emergent adverse events are events with an onset after the administration of the first dose of protocol-specified therapy.

The subject incidence of AEs will be summarized for all treatment-emergent AEs, serious AEs, AEs leading to withdrawal of protocol-specified therapy, and fatal AEs.

Subject incidence of all treatment-emergent AEs, serious AEs, AEs leading to withdrawal of IP, and fatal AEs will be tabulated by system organ class and preferred term in descending order of frequency; similar summaries will be repeated for EOIs.

Approved

Time to onset and duration of selected EOs (infection and neurologic events) may also be summarized.

For phase 3, a summary of treatment-emergent AEs with at least a 5% higher subject incidence in 1 treatment arm compared to the other will be presented by preferred term. This summary will be repeated for serious AEs using a 10% threshold.

A summary of treatment-emergent AEs will be tabulated by system organ class, preferred term, and worst grade.

Subgroup analyses (if there is a medical or regulatory rationale) will be presented by system organ class and preferred term in descending order of frequency. All races (if appropriate) with less than 5% of the total subjects will be pooled together for summary purposes.

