
	Safety follow-up	HSCT	Long-term follow-up	
	Approximately 30 days after last dose of blinatumomab or the last day of the last cycle of IC chemotherapy	Within 14 days prior to conditioning regimen	≤ 2 years after EOT: Every 3 months (± 14 days) ^a	> 2 years after EOT: Every 6 months (± 28 days) ^b
General Assessments				
ECOG Performance Status	X			
Medical history and prior therapies	← Continuous from start of treatment →			
Vital signs	X			
Weight	X			
Physical examination	X			
Neurological exam	X			
Clinical tumor assessment	X	X	X	
Serious adverse events	X		X ^c	
Disease related events	X			
Concomitant medications	X		Lymphoma treatment only	
Subject-reported clinical outcome assessment ^d	X			
HSCT Summary ^e			X ^f	
Local Laboratory Assessments				
Hematology	X			
Chemistry	X			
Coagulation	X			
Immunoglobulins	X			
LDH	X	X	X	
Central Laboratory Assessments				
Bone Marrow ^g		per institutional standard		
Pathology tumor block or slides ^h		Collect if lymphoma relapse		
Plasma sample ⁱ		X	X	
Anti-blinatumomab antibodies	X ^j			
Radiographic Assessments				
PET/CT ^k		per institutional standard		

Footnotes defined on the next page.

Approved

CT=computed tomography; CT-DNA=circulating tumor DNA; ECOG=Eastern Cooperative Oncology Group; EOT=end of treatment; IC=investigator's choice; LDH=; PET=positron emission tomography;

^a To occur in person every 3 months (calculated from safety follow up) until completion of a 2-year period after treatment

^b To occur in person or by telephone call every 6 months (\pm 28 days) until study completion

^c Only adverse events possibly related to blinatumomab will be collected

^d Phase 3 only

^e HSCT summary will include completion of details about mobilization, engraftment, specific toxicities, infectious complications

^f HSCT summary is at first post HSCT visit

^g Bone marrow biopsy is not required if PET scan is negative and if not otherwise clinically necessary by investigator discretion

ⁱ At the time of relapse

^j Plasma must be collected, processed, and frozen within 4 hours of phlebotomy

^k For subjects previously randomized to blinatumomab only

^l Based on any scans performed, response is to be assessed locally according to institutional standard and according to the Lugano classification. Any radiographic indication of progression should be followed-up by biopsy.

Approved

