9.2.2 Adverse Events

9.2.2.1 Reporting Procedures for Adverse Events That Do Not Meet Serious Criteria

The investigator is responsible for ensuring that all adverse events observed by the investigator or reported by the subject that occur from the first dose of IP through the safety follow-up visit are reported using the Event CRF. Adverse events considered by the investigator to be possibly related to blinatumomab will be reported from the beginning of transplant conditioning during the long-term follow up until completion of a 2-year period after treatment.

Approved

The investigator must assign the following adverse event attributes:

- Adverse event diagnosis or syndrome(s), if known (if not known, signs or symptoms),
- Dates of onset and resolution (if resolved),
- Severity [and/or toxicity per protocol],
- Assessment of relatedness to blinatumomab or protocol required medication or medical device, and
- Action taken.

The adverse event grading scale used will be the CTCAE. The grading scale used in this study is described in [Appendix A](#).

The investigator must assess whether the adverse event is possibly related to blinatumomab. This relationship is indicated by a “yes” or “no” response to the question: Is there a reasonable possibility that the event may have been caused by the investigational medicinal product?

The investigator must assess whether the adverse event is possibly related to any study-mandated activity (eg, protocol-required therapies). This relationship is indicated by a “yes” or “no” response to the question: “Is there a reasonable possibility that the event may have been caused by a study activity (eg, protocol-required therapies), and/or procedure”?

The investigator is responsible for reviewing laboratory test results and determining whether an abnormal value in an individual study subject represents a change from the subject’s baseline values. All grade 3 and grade 4 laboratory values should be recorded as adverse events. In addition, if signs or symptoms are associated with a laboratory abnormality, the signs/symptoms and the laboratory abnormality should all be recorded as adverse events. The laboratory abnormality and any signs/symptoms should be graded according to their own CTCAE criteria.

The Investigator is expected to follow reported adverse events until stabilization or reversibility.

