9.2.2.2 Reporting Procedures for Serious Adverse Events

The investigator is responsible for ensuring that all serious adverse events observed by the investigator or reported by the subject that occur after signing of the informed consent through safety follow-up are recorded in the subject’s medical record and are submitted to Amgen. In addition, blinatumomab related serious adverse events will be reported during the long term follow-up. All serious adverse events must be submitted to Amgen within 24 hours following the investigator’s knowledge of the event via the Event CRF.

If the electronic data capture (EDC) system is unavailable to the site staff to report the serious adverse event, the information is to be reported to Amgen via an electronic Serious Adverse Event Contingency Report Form within 24 hours of the investigator's knowledge of the event. See [Appendix B](#) for a sample of the Serious Adverse Event Worksheet /electronic Serious Adverse Event Contingency Report Form. For EDC studies where the first notification of a Serious Adverse Event is reported to Amgen via the eSerious Adverse Event Contingency Report Form, the data must be entered into the EDC system when the system is again available.

The investigator must assess whether the serious adverse event is possibly related to blinatumomab and/or other protocol-required therapies. This relationship is indicated by a "yes" or "no" response to the question: Is there a reasonable possibility that the event may have been caused by the IP?

The investigator is expected to follow reported serious adverse events until stabilization or reversibility.

New information relating to a previously reported serious adverse event must be submitted to Amgen. All new information for serious adverse events must be sent to Amgen within 24 hours following knowledge of the new information. If specifically requested, the investigator may need to provide additional follow-up information, such as discharge summaries, medical records, or extracts from the medical records.

Information provided about the serious adverse event must be consistent with that recorded on the Event CRF.

If a subject is permanently withdrawn from protocol-required therapies because of a serious adverse event, this information must be submitted to Amgen.

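### Phase 3 treatment-emergent adverse events have no end date, yet after the safety follow-up visit only blinatumomab-related events are routinely collected, so late events can enter the between-arm tables from one arm only

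*Protocol*

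**What the plan says.** **Definition and tables (Protocol 10.5.4.1).** "Treatment-emergent adverse events are events with an onset after the administration of the first dose of protocol-specified therapy". No end is given. The section then states: "All adverse event tables will be summarized by treatment group". It adds a between-arm table: "For phase 3, a summary of treatment-emergent AEs with at least a 5% higher subject incidence in 1 treatment arm compared to the other". The same table is repeated for serious events with a 10% threshold.

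**General collection.** Under 9.2.2.1, non-serious events that "occur from the first dose of IP through the safety follow-up visit are reported using the Event CRF". Section 9.2.2.2 likewise ends general serious-event reporting at safety follow-up.

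**Late collection.**
- Non-serious events (9.2.2.1): only those the investigator considers possibly related to blinatumomab, and only "from the beginning of transplant conditioning during the long-term follow up until completion of a 2-year period after treatment".
- Serious events (9.2.2.2): "blinatumomab related serious adverse events will be reported during the long term follow-up".
- Table 9, footnote c, on the serious-event row under long-term follow-up: "Only adverse events possibly related to blinatumomab will be collected".

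No section sets up matching late collection of events related to IC chemotherapy.

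**SAP.** Section 6.1 closes the treatment-emergent window 30 days after the end of blinatumomab, for serious events too. That SAP describes a single-arm blinatumomab study. It has no IC arm and no between-arm table.

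**The concern.** A between-arm incidence table is interpretable only if both arms are observed under the same rule. Here the analysis definition is open-ended and the data feeding it are not symmetric. A related event a year after blinatumomab is collected and meets the definition. The same event a year after IC chemotherapy is not routinely collected and so cannot be counted.

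Comparing the two safety profiles is a phase 3 secondary objective (Protocol 1.2.2). The difference tables are the most exposed, because a preferred term is listed once the arms differ by a fixed amount. A term could be listed because of what was collected and not because of what occurred.

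**Working it through.** **1. The plan's own follow-up figure.** Protocol 10.4.4 gives 33 months maximum follow-up. Accrual takes 296 / 14.5 = 20.4 months (the plan uses 21), and 21 + 12 = 33 months. The figure reproduces, so early enrollees can reach two years after treatment.

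**2. Windows to the safety follow-up visit.** Inputs: 56 infusion days in blinatumomab cycle 1; up to three 28-day IC cycles; the visit 30 days later, taken after the last dose for blinatumomab and after the last day of the last cycle for IC (Table 9, 7.2.4).
- Blinatumomab: 56 + 30 = 86 days.
- IC: 3 × 28 + 30 = up to 114 days.
- With optional treatment: blinatumomab 70 + (14 to 28) + 28 + 30 = 142 to 156 days; IC 6 × 28 + 30 = up to 198 days.

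Up to this visit the IC window can be the longer one.

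**3. Maximum window after it, blinatumomab arm.** Two years after the last dose of cycle 1 is day 56 + 730.5 = 786.5, or 25.8 months. Beyond the visit that is 786.5 − 86 = 700.5 days, or 23.0 months. Section 9.2.2.2 states no two-year cap for serious events, but Table 9 appears to mark them only in the column for the first two years. I use two years for both.

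**4. Average window, allowing for death.** Exponential survival with the planned median of 6.7 months gives λ = ln 2 / 6.7 = 0.1035 per month.
- Alive at the visit (2.83 months): exp(−0.1035 × 2.83) = 0.747.
- Alive at 25.8 months: 0.069.
- Person-months before the visit: (1 − 0.747) / 0.1035 = 2.4.
- Person-months after it: (0.747 − 0.069) / 0.1035 = 6.5, about 2.7 times the earlier amount.

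This assumes that everyone can be followed for two years. If follow-up stops at month 26, with uniform accrual over 21 months, potential follow-up runs from 5 to 26 months. Mean survival at the cut-off is then (exp(−5λ) − exp(−26λ)) / (21λ) = 0.243, and the average falls to (0.747 − 0.243) / 0.1035 = 4.9 person-months.

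**5. Subjects needed to cross a threshold.** Assume 148 treated per arm (296 / 2), equal incidence of a term up to the visit, and thresholds in percentage points.
- 5%: 148 × 0.05 = 7.4, so 8 subjects (8 / 148 = 5.4 points).
- 10%, serious: 148 × 0.10 = 14.8, so 15 subjects (10.1 points).

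Each must have the same preferred term late and not earlier, because the measure is subject incidence.

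**6. Illustration with assumed rates.** The documents give no late-event rate. For an assumed monthly rate r of first late related events, with everyone at risk over the whole 23.0 months, the added incidence is 0.747 × r / (r + λ) × (1 − exp(−(r + λ) × 23.0)).

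| Assumed r per month | Points added, blinatumomab | Points added, IC |
|---|---|---|
| 0.5% | 3.2 | 0 |
| 1% | 6.1 | 0 |
| 2% | 11.4 | 0 |

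These are high-end figures. Late non-serious events are collected only from transplant conditioning, so most subjects may not be at risk for the whole window. To bear on a threshold, the rate must also belong to a single preferred term.

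**The case against.** **Phase 3 may not run.** Amendment 2 adds the option of not proceeding, and its replacement schema in the summary of changes carries a note that phase 3 is cancelled. The SAP covers phase 2 only, so a phase 3 SAP would still have to be written, and it could set the window. This lowers the urgency and stands. Yet Protocol 3.1 and section 10 still specify phase 3, and 10.5.4.1 is the only definition that reaches its tables.

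**The SAP already has a 30-day limit.** It does, and SAP section 11 does not list it as a change, which suggests the sponsor may read the protocol as bounded. But the limit is tied to the end of blinatumomab and gives no end date for IC. It answers the point for phase 2 only.

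**The two years are a ceiling.** This stands. Late events must be judged related, non-serious ones count only from conditioning, and most subjects are expected to have died by then.

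**Late IC toxicity is not invisible.** A reader might infer that it is never seen. The documents do not support that. The HSCT summary at about 100 days records complications in either arm (7.2.6, Table 9). Cause of death is sought for all subjects (7.3.17), 100-day non-relapse mortality is summarised by treatment group (10.5.3), and section 9.2.2.3 permits later serious-event reports. What is missing is routine late adverse-event collection on IC, and these other routes do not supply it.

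**The imbalance before the visit runs the other way.** It can, at up to 114 days on IC against 86. That does not cancel the late asymmetry, but it does confirm that no common window is defined.

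**Conclusion.** The point holds in a limited form. As written, late blinatumomab-related events are treatment-emergent and enter the between-arm adverse event and serious adverse event tables, with no matching routine collection on IC. This late component can add only to the blinatumomab arm.

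Its size cannot be fixed from the documents. The extra window is at most about 23 months and averages about 6.5 person-months per subject at the planned median survival, or less once the final analysis cuts follow-up short. Crossing a threshold from equal rates takes about 8 subjects (adverse events) or 15 (serious events) with the same late term. These figures rest on exponential survival, 148 treated per arm and thresholds read as percentage points.

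A reader might infer that the tables as a whole are biased against blinatumomab by design. The documents do not support that: the earlier window can favour blinatumomab, the tables are descriptive, and no late-event rate is given. The point matters only if phase 3 is run. If it is, the wording should be settled before any between-arm safety table is produced.

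**What to change.** In Protocol 10.5.4.1, and in any phase 3 SAP:

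1. End the treatment-emergent window at the safety follow-up visit in both arms for all between-arm adverse event and serious adverse event tables, including the 5% and 10% difference tables. State a default end day for subjects who have no such visit.
2. Reconcile the IC anchor for that visit. Section 3.1 counts 30 days from the last dose of IC chemotherapy, while Table 9 and 7.2.4 count from the last day of the last cycle. A separate cut-off of 30 days after last dose should not be written into the tables while these differ, since it could drop IC events that were collected.
3. List later blinatumomab-related events separately, labelled as collected in one arm only.

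The cost is wording in the statistical section, one reconciled visit definition and one extra listing. Late blinatumomab events leave the comparative tables but remain reported. Late collection at sites need not change. A common stopping rule still leaves somewhat different window lengths by arm, so exposure time should be shown beside the incidences.
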